5.2.2. Randomization and Treatment Visit (V1, Week 0)

5.2.2.1 Vital signs monitoring, check EKG and biochemistry results and confirm eligibility of patients.

5.2.2.2 A randomization number is given to eligible patient.

5.2.2.3 Inform patient of the possible adverse events.

5.2.2.4 Review three-day voiding diary.

5.2.2.5 Collect 30 ml urine for analysis of the urinary NGF and cytokines levels.

5.2.2.6 LESW given.

5.2.3. Treatment Visit (V2, Week 1, 1 week \pm 3 days after the V1 treatment day)

5.2.3.1 Vital signs monitoring, and confirm eligibility of patients.

5.2.3.2 LESW given.

5.2.4. Treatment Visit (V3, Week 2, 1 week \pm 3 days after the V2 treatment day)

5.2.4.1 Vital signs monitoring, and confirm eligibility of patients.

5.2.4.2 LESW given.

5.2.5. Treatment Visit (V4, Week 3, 1 week \pm 3 days after the V3 treatment day)

5.2.5.1 Vital signs monitoring, and confirm eligibility of patients.

5.2.5.2 LESW given.

5.2.5.3 Dispense three-day voiding diary to record for 3 days before the next visit day.

5.2.6 Evaluation Visit I (V5, 1 week \pm 3 days after the V4 treatment day)

5.2.6.1 Review patients voiding diary for urinary frequency, functional bladder capacity, and record reported VAS, O'Leary-Sant symptom score, and GRA.

5.2.6.2 Vital signs monitoring and record adverse events.

5.2.6.3 Check urinalysis for urinary tract infection if patient has symptoms.

5.2.6.4 Check uroflowmetry for maximum flow rate, voided volume, and PVR volume.

5.2.6.5 Appointment for the next visit at 1 month \pm 3 days after the V4.

5.2.6.6 Dispense three-day voiding diary to record for 3 days before the next visit day.

5.2.6.7 Collect 30 ml urine for analysis of the urinary NGF and cytokines levels.

5.2.7 Evaluation Visit II (Primary end-point, V6, 1 month \pm 7 days after the V4)

5.2.7.1 Review patients voiding diary for urinary frequency, functional bladder capacity, and record reported VAS, O'Leary-Sant symptom score, and GRA.

5.2.7.2 Vital signs monitoring and record adverse events.

5.2.7.3 Check urinalysis for urinary tract infection if patient has symptoms suggestive of urinary tract infection.

5.2.7.4 Perform Uroflowmetry study for maximum flow rate, voided volume and PVR volume.

5.2.7.5 Collect 30 ml urine for analysis of the urinary NGF and cytokines levels.

5.2.8 Evaluation Visit III (V7, 3 month \pm 7 days after the V4)

5.2.8.1 Review patients voiding diary for urinary frequency, functional bladder capacity, and record reported VAS, O'Leary-Sant symptom score, and GRA.

5.2.8.2 Vital signs monitoring and record adverse events.

5.2.8.3 Check urinalysis for urinary tract infection if patient has symptoms suggestive of urinary tract infection.

5.2.8.4 Perform Uroflowmetry study for maximum flow rate, voided volume and PVR volume.

5.2.8.5 Collect 30 ml urine for analysis of the urinary NGF and cytokines levels.

5.2.8.6 Patients who do not respond to treatment will be provided with repeat LESW treatment optionally.

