- (2) Global response assessment (GRA) of therapeutic result by the patient (categorized from -3 to +3, indicating markedly worse to markedly improved) at 2 months after the treatment day.
- (3) Net changes of the maximum flow rate, voided volume, and PVR from baseline to 2 months after the treatment day.
- (4) Changes of urinary nerve growth factor and cytokines level from baseline to 2 months after treatment day.

Effectiveness of treatment was considered if the patient has an improved GRA by 2 scales at the primary and secondary end-point assessments.

Patients who are not effective to the treatment at 2 months will receive repeated LESW treatment.

Safety

- (1) Local adverse event incidences (hematuria, miction pain, UTI, urinary retention) are reported.
- (2) Any systemic adverse event occurring after LESW will be asked to report and patients will be properly investigated and treated. The cause for systemic adverse event may be not related with LESW treatment.

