6. ADVERSE EVENTS

6.1. Introduction

An adverse event is defined as a new medical condition or worsening of the existing condition following or during the trial medicinal exposure (including placebo). However, a deterioration of medical condition can be in doubt of either an adverse event or being due to the lack of efficacy of

the treatment. Situations as such should be considered as a lack of efficacy unless the sponsor or the investigators or the regulatory authorities state to the contrary.

All adverse events occurring during the study should be documented on Adverse Event Forms. One Adverse Event Form should be filled out for each adverse event. All items on the form should be completed and feedback to National Reporting System of Adverse Drug Reaction in Taiwan (ADR) as soon as possible. For serious adverse events, a preliminary Adverse Event Form must be returned to the ADR immediately (within 24 hours), with complete and/or new information submitted to the ADR as soon as it becomes known.

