7.2 Analysis

The statistical objective of this study is to demonstrate that the efficacy of LESW is superior to placebo with respect to the decreases of O'Leary-Sant symptom score, VAS, increase in functional bladder capacity and improvement in GRA. The safety profile of LESW or placebo for the either group of intravesical treatment of patients with IC/BPS will also be confirmed.

Primary Efficacy Endpoint

The efficacy of LESW treatment will be evaluated for:

(1) Net change of the O'Leary-Sant symptom score from baseline to 1 month after the treatment day.

Secondary Efficacy Endpoint

The efficacy of LESW will be evaluated for:

- (1)Net change of the following parameters from baseline to 1 month after the treatment day: Visual analog score (VAS) for pain (from 0 to 10), functional bladder capacity (FBC), voiding frequency at daytime and voiding frequency at night time as recorded in 3-day voiding diary.
- (2) Global response assessment (GRA) of satisfaction by the patient (categorized into -3, -2, -1, 0, 1, 2, 3, indicating markedly worse to markedly improved) at 1 month after the treatment day. An improvement of GRA by 2 scales at 1 month is considered effective.
- (3) Net changes of the maximum flow rate, voided volume and PVR from baseline to 1 month after the treatment day.

Voiding frequency at daytime and nighttime is measured as mean of the three-day voiding diary preceding the scheduled visit and the record days are 3 days.

Net change of each efficacy item will be analyzed by paired t-test between baseline and post-treatment in the treatment group and controlled group. The net changes of each efficacy item will be analyzed by ANOVA test to compare between treatment group and controlled groups. The global response assessment by the patients will be analyzed by Fisher exact test between the treatment and controlled groups.

All efficacy variables will be reported of respective point estimated and 95% confidence interval. Comparison tests will be reported of respective p value.

Secondary Safety Endpoints

- (1) Local adverse event incidences (hematuria, micturition pain, UTI, urinary retention) will be reported by both treatment group and controlled group and by physiological systems as appropriate. Incidence of adverse events and the categories of adverse event severity between treatments will be analyzed. The coding system used will be COSTART.

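### Adverse events are compared by arm with no cut-off at the repeat LESW course, which neither passage limits to one arm and whose timing, status and content are unsettled

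*Protocol*

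**What the plan says.** Protocol Section 2, under the 3-month follow-up, states: "Patients who are not effective to the treatment at 2 months will receive repeated LESW treatment". Protocol Section 5.2.8, the last visit in the schedule (V7), ends with: "Patients who do not respond to treatment will be provided with repeat LESW treatment optionally". Neither sentence names an arm.

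At V7 the protocol lists "5.2.8.2 Vital signs monitoring and record adverse events" ahead of the retreatment item. No later visit appears. Outside the visits there are general duties:

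- Section 6.1: "All adverse events occurring during the study should be documented on Adverse Event Forms".
- Section 2 (follow-up safety): "Any systemic adverse event occurring after LESW will be asked to report and patients will be properly investigated and treated".
- Section 6.3: serious events are reported within 24 hours and followed, as far as possible, to outcome.

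On analysis, SAP 7.1 confines safety to the ITT set. SAP 7.2 says that local adverse events "will be reported by both treatment group and controlled group" and adds: "Incidence of adverse events and the categories of adverse event severity between treatments will be analyzed". It gives no exposure window, no rule for events after retreatment and no category for retreated patients.

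**The concern.** A between-arm safety comparison is interpretable only while the arms receive different treatments. If placebo-assigned patients start active LESW and their later events stay in the control column, the control rate rises for a reason unrelated to placebo and the apparent excess risk of LESW falls. For a safety comparison, that is the unsafe direction.

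If the repeat course instead starts after the last scheduled recording, the randomized comparison is protected. The trial then has no scheduled means of describing safety during that course. The stated objective covers safety as well as efficacy, although the safety endpoints are secondary.

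**Working it through.** The plan gives no figure to reproduce on this point: no adverse-event, non-response or retreatment rate appears in either document. The main check is to set the two passages side by side.

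| | Section 2, follow-up | Section 5.2.8, last item |
|---|---|---|
| When | 2 months; no visit is scheduled then (V6 is at 1 month, V7 at 3 months) | At V7, 3 months ± 7 days after V4 |
| Status | Will be given | Optional |
| Arm | Not limited | Not limited |
| Active or assigned treatment | Not stated | Not stated |
| Number of sessions | Not stated | Not stated |
| Relative to V7 event recording | Before | Listed after |

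**Section 2 timing, active course.** V7 recording follows the start of active shocks in retreated placebo patients. SAP 7.2 has only two columns and no cut-off, so these events fall under control.

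**Section 5.2.8 timing.** Scheduled data through V7 precede the repeat course, so misattribution in them is zero. Scheduled adverse-event recording appears only at V5, V6 and V7. The V1 to V4 treatment-visit lists contain no such item, so a repeat course modelled on them would not supply one.

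**Illustration for the Section 2 timing only; every rate is assumed.** Let a be the event risk per LESW course, b the risk on placebo, r and s the shares of placebo and LESW patients retreated. Assume an active repeat course, independent risks, all repeat-course events seen by V7, and counting by assigned arm.

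- Apparent control incidence: P = 1 − (1 − b)(1 − r·a)
- Apparent LESW incidence: L = 1 − (1 − a)(1 − s·a)

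With a = 0.20 and b = 0.04, the true difference is 16 points.

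- r = 0.7: P = 1 − 0.96 × 0.86 = 17.4%
- s = 0.3: L = 1 − 0.80 × 0.94 = 24.8%; difference 24.8 − 17.4 = 7.4 points
- s = 0.5: L = 1 − 0.80 × 0.90 = 28.0%; difference 28.0 − 17.4 = 10.6 points
- r = 0.5: P = 1 − 0.96 × 0.90 = 13.6%; difference 11.2 to 14.4 points
- r = 0.8: P = 1 − 0.96 × 0.84 = 19.4%; difference 5.4 to 8.6 points

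A second set (b = 0.05, a = 0.20, r = 0.6, s = 0.4) gives P = 1 − 0.95 × 0.88 = 16.4% and L = 1 − 0.80 × 0.92 = 26.4%, so 15.0 points becomes 10.0.

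The shrinkage equals (1 − b)·r·a − (1 − a)·s·a. When a exceeds b it is positive whenever placebo patients are retreated at least as often as LESW patients. If V7 captures only part of the repeat-course events, in equal proportion in both arms, the shrinkage falls in that proportion. A cut-off at the first repeat session sets r and s to zero in the comparison and restores the true difference.

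**The case against.** The strongest reply is that the visit schedule is the operative text. It places the course after V7 recording and has no 2-month visit at which the Section 2 rule could be applied. On that reading no scheduled comparison is contaminated. This stands as one reading, but Section 2 states its rule without qualification, so the contradiction remains.

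A reader might also infer several stronger things that the documents do not support:

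- *Repeat-course events are never collected.* The general duties in Sections 2, 6.1 and 6.3 may reach them. Sections 3 and 5.1 also attach vital signs before and 30 minutes after treatment to the procedure, and Section 5.1 adds an enquiry about pain. What is missing is scheduled collection after V7 and a defined end to the collection period.
- *Placebo patients certainly cross over.* The visit list calls the session LESW for both arms, the trial is double-blind, and no unblinding step is described. Active LESW is the natural reading of the repeat course, but it is not stated.
- *Exposure doubles.* Four sessions of 2000 shocks make 8,000. The 16,000 that a second identical course would give is an assumption, since the number of repeat sessions is not stated.
- *Counting is by assigned arm.* This is inferred from the ITT set and the two-group report. No as-randomized or as-treated rule is written.

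Finally, the numbers are small. With 25 per group, 20% against 4% is 5 patients against 1 (two-sided Fisher p = 0.19) before any crossover, and the SAP names no test for adverse events. No planned safety conclusion clearly turns on this point. That limits its weight, but does not remove the need for a rule.

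**Conclusion.** The point holds in a conditional form. The plan does not settle what the repeat course is, when it occurs or whether it is optional, and the SAP does not say that the between-arm adverse-event comparison stops when it starts.

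- Under the Section 2 timing with an active course counted by assigned arm, the comparison is biased toward no difference, provided LESW carries the higher risk and placebo patients are retreated at least as often. The true size is unknown. At 70% placebo and 30% to 50% LESW retreatment, the assumed rates shrink 16 points to about 7 to 11. The loss of 5.4 to 8.6 points is about 1.4 to 2.2 patients of 25.
- Under the Section 5.2.8 timing, there is no bias in scheduled data through V7; the gap is the unscheduled and open-ended collection afterwards.

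It would be wrong to read this as a threat to the main result: the 1-month primary endpoint (V6) precedes retreatment under either passage. The change should be made, but the trial's primary conclusion does not depend on it.

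**What to change.** In SAP 7.2, end each patient's randomized adverse-event comparison at V7 or at the first repeat session, whichever comes first. List later events separately, by assigned arm and number of active sessions actually received.

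In the protocol, the sponsor should reconcile Section 2 with Section 5.2.8 on timing and on whether the course is optional, and say whether it is active LESW. No retreatment rule is proposed here. The protocol should also state that adverse-event recording continues through the repeat course, and when it ends.

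The SAP rule works under either timing. The cost is a few lines of text, one extra safety table, and adverse-event enquiry at sessions that patients already attend.

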5.3. Withdrawal Criteria

Patients with any of the following conditions may be withdrawn from the trial:

- 5.3.1. Patients decide to withdraw their consent at any time-point.
- 5.3.2. Patients indicate the status of lack of efficacy which is of clinical significance judged by the investigators that may lead to permanent damage to the patients.
- 5.3.3. Investigators consider that there is of safety concerns for the patients to remain in the trial (such as development severe medical disease).
- 5.3.4. Lost of follow-up or death.

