7. STATISTICAL ANALYSIS

7.1. Evaluability

Patients receiving baseline screening and treatment will be considered as intent-to-treat (ITT) population. The ITT population with the following conditions will be considered as per-protocol (PP) population:

- 1. Not taking any prohibited medications
- 2. Fulfilling all entry criteria
- 3. Have treatment visit and post-treatment evaluations on the primary endpoint

The efficacy evaluation will be performed on both the ITT and PP datasets while the safety evaluations will be performed only on the ITT datasets. The primary conclusions will be made for the primary and secondary endpoints on the ITT patients.

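### Section 5.3 makes harmful lack of efficacy a ground for leaving the trial, with no route for stopping sessions and staying in follow-up, so a poor result can cost an ITT patient the primary score

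*Protocol*

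**What the plan says.** Protocol 5.3 has one list and one action: "Patients with any of the following conditions may be withdrawn from the trial". Its second ground is "lack of efficacy which is of clinical significance judged by the investigators that may lead to permanent damage to the patients". Its third reads "Investigators consider that there is of safety concerns for the patients to remain in the trial", with development of a severe disease as the example. The other grounds are withdrawn consent, and loss to follow-up or death.

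Protocol 5.2 schedules four weekly sessions, V1 (labelled Week 0) to V4 (labelled Week 3). The follow-up visits open with "5.2.6 Evaluation Visit I (V5, 1 week", "5.2.7 Evaluation Visit II (Primary end-point, V6, 1 month" and "5.2.8 Evaluation Visit III (V7, 3 month", and each heading then counts its time from V4. The O'Leary-Sant score is recorded at screening (5.2.1.10) and next at V5; none is listed at V1 to V4. The voiding diary for V5 is handed out at V4 (5.2.5.3).

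SAP 7.1 says "Patients receiving baseline screening and treatment will be considered as intent-to-treat (ITT) population" and rests the primary conclusions on that population. SAP 7.2 compares net change between arms by ANOVA. SAP 7.3 treats incomplete observations as missing and estimates nothing.

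**The concern.** Withdrawn consent, loss to follow-up and death make further scores unobtainable. Harmful lack of efficacy does not: it is a reason to stop the sessions and change treatment, and the patient can usually still complete a questionnaire. Because 5.3 ties this ground to leaving the trial, a score that could have been collected is lost, and it is lost because the patient did badly.

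An analysis of observed net changes cannot correct for that. Removing a poor result from placebo makes placebo look better and shrinks the difference; removing one from LESW enlarges it. Enrolment of about 50 for 25 evaluable patients per group (SAP 7.4) leaves no allowance for lost scores.

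**Working it through.** **1. Following the patient through the text**

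- *Withdrawn under 5.3.2 before V4.* The only O'Leary-Sant score is the one from screening. V5, V6 and V7 have no stated date, because V4 did not happen. The diary for V5 was never handed out.
- *Withdrawn under 5.3.2 after V4 but before V6.* The visits are dated, but the patient has left the trial. A V5 score may exist; the primary one-month score does not.
- *Analysis set.* SAP 7.1 does not say whether treatment means any session or the whole course. If any session, the patient is in ITT. Net change to one month cannot be computed and SAP 7.3 supplies no value, so the patient is not in the primary ANOVA.

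**2. Plan figures used**

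From SAP 7.4: mean decrease 8.0 (LESW) and 5.0 (placebo), SD 5.0, 25 per arm. Planned difference = 8.0 − 5.0 = 3.0. Standard error = 5.0 × √(2/25) = 1.414.

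The 25 per arm is taken only as the arm size. It does not reproduce from its own inputs: 2 × (1.960 + 0.842)² × 5.0² / 3.0² = 43.6, or 44 per arm, for two-sided α = 0.05 and power 0.80. That is a separate matter and nothing below depends on it.

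**3. Illustration: what a lost score does to the difference**

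Assumption: each full arm of 25 would have had its planned mean *m*, and *k* = 1 or 2 patients with zero change are lost. The mean of those remaining is 25*m* / (25 − *k*).

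| Lost | Mean of remaining | Difference | Shift | Shift / SE |
|---|---|---|---|---|
| 1 placebo | 125/24 = 5.208 | 2.792 | −0.208 | −0.15 |
| 2 placebo | 125/23 = 5.435 | 2.565 | −0.435 | −0.31 |
| 1 LESW | 200/24 = 8.333 | 3.333 | +0.333 | +0.24 |
| 2 LESW | 200/23 = 8.696 | 3.696 | +0.696 | +0.49 |
| 1 from each | 8.333 and 5.208 | 3.125 | +0.125 | +0.09 |

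For one lost patient with change *c*, the shift has size (*m* − *c*)/24. A patient who had worsened would therefore move the difference further, by 1/24 = 0.042 for each point of worsening.

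**4. Precision**

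By the normal approximation, power at the planned difference is 56.4% with 25 per arm, 55.6% with one patient missing from one arm, and 54.6% with two missing. The loss of information is small; the issue is bias.

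**The case against.** The case against is that this is a narrow gap, and much of that stands.

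- *Withdrawal is optional.* The wording is permissive, so a reader who infers that 5.3 forces these patients out goes too far. But an investigator who keeps such a patient has no procedure to follow and, before V4, no visit dates.
- *Ground 5.3.3 might be read as a second route of the same kind.* The text does not support that. It concerns whether staying in the trial is safe, not whether sessions should continue, and for some patients leaving will be right.
- *Section 6.1 might be read as widening 5.3.2.* Of a deterioration of doubtful cause it says "Situations as such should be considered as a lack of efficacy". That sentence settles whether the event is classed as an adverse event, and investigators may decide otherwise. Ground 5.3.2 still needs their judgement and a risk of permanent damage.
- *Ordinary non-responders might be thought lost too.* They are not. They stay in follow-up and may be offered repeat LESW (Protocol 2 and 5.2.8.6). Zero change in the illustration is ordinary non-response, so the number of patients expected at or below zero would not measure the 5.3.2 group.
- *A date could be improvised.* V4 carries a Week 3 label, and the endpoint is set one month after a treatment day that is not identified. Both are possible anchors, but the plan does not say which applies when V4 is missed, and sites in a multicenter trial could choose differently.
- *The group is very small.* Eligibility requires more than six months of symptoms, and the sessions span about three weeks. Permanent damage from lack of efficacy in that time should be rare.

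What survives is that 5.3.2, used as written, removes a patient from the primary analysis because of a poor result, and no text provides the alternative.

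**Conclusion.** The point holds as a limited one. The rule in 5.3.2 can cause outcome-related loss of the primary score, and for a patient who stops before V4 the schedule gives no date on which to collect it. Placing that patient in ITT rests on reading treatment in SAP 7.1 as any session. If the full course is meant, a patient who stops before V4 falls outside ITT altogether, and the primary comparison still lacks the score.

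The documents give no withdrawal rate, and few patients are likely to be affected. Under the zero-change assumption each lost patient moves the difference by 0.15 to 0.25 standard errors (0.208/1.414 for one lost from placebo; 0.696/2/1.414 per patient for two lost from LESW). It would be wrong to infer that the result is biased in favour of LESW: the direction depends on which arm loses patients, and losses from both arms partly cancel. The reason to act is that an uncollected score cannot be recovered and collecting it is cheap.

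**What to change.** 1. In Protocol 5.3, make 5.3.2 a ground for stopping sessions, and 5.3.3 likewise only where the investigator judges follow-up safe. Ask these patients to attend the existing V5, V6 and V7 assessments unless they refuse. Keep withdrawal from the trial for withdrawn consent, loss to follow-up, death, or unsafe follow-up.
2. In 5.2.6 to 5.2.8, state that when V4 does not take place, V5 to V7 are dated from the nominal Week 3 day (V1 + 3 weeks), with the windows in those headings. Dispense the V5 voiding diary when sessions stop.
3. Record any prohibited treatment started afterwards, with its start date, and keep the patient's scores in ITT. Under SAP 7.1 such treatment already costs only per-protocol status. A clause there should say that any session counts as treatment.

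Decisions on when to stop and how to treat stay with the investigator.

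The cost is a few lines and no new visits or procedures. The nominal day is an approximation, since a completer's V4 can itself fall up to 3 × 3 = 9 days from V1 + 3 weeks. The main downside is that some ITT scores will follow stopped sessions or other treatment. The result then reflects assignment to LESW and not completion of the course, and other treatment may hide part of a poor result; the start dates show which scores these are. The consent pages were not available for review, so the sponsor should check that they cover follow-up after sessions stop.
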